7.2.3. Rationale for the unbalanced allocation approach (precision trial)

Prior trials evaluating the impact of HCV adherence support interventions among PWID have used standard approaches that randomize groups of individuals to different interventions or to a single intervention vs. the standard of care. This approach assumes that all of those assigned to an intervention have the same need for the intervention and the potential to benefit equally from the intervention. However, while the data do support that at least some PWID will need additional support to achieve cure, there are structural barriers (e.g., infrastructure, human capital) that limit the capacity to provide intensive support to all those treated, particularly in settings with high burden.^{31,34} Identifying who can be cured with minimal intervention and who will need more support can potentially improve efficiencies.

This protocol utilizes a "precision" approach to allocating treatment support based on need allowing us to estimate efficacy within strata of risk for treatment failure (minimal/elevated risk) while still allowing estimation of the average treatment effect. This approach is similar to stratified randomization with the modification that treatment allocation is not equal across strata. This targeted randomization actually induces confounding (because the prognostic score is based on factors that influence the outcome) that needs to be accounted for in the analysis (**see Section 15**). However, because of randomization, the factors used in determining propensity for failure will be balanced in expectation, as this is analogous to a propensity score, which balances included covariates. Thus, using a single approach, we can answer multiple questions related to both the efficacy of the support strategy for persons at different levels of risk for failure as well as the impact in the total population of a particular support strategy.

7.2.4. Potential impact of trial

Both of the behavioral interventions in this trial rely on the support of nurses and peer/community health workers. In many LMIC settings, high healthcare costs, infrastructure gaps and general shortages in physicians and nurses have led to increased use of community health workers to deliver care for HIV, tuberculosis and increasingly non-communicable diseases.⁷⁷⁻⁷⁹ Indeed, the WHO has supported such a strategy for HIV in response to issues around shortages. In general community health workers are members of communities where they work and are supported by the health system but tend to have less structured training than nurses and others in the formal health care system. The idea is that these health workers provide a bridge between the health care system and the community, deliver low cost primary health care services and can facilitate

engagement in and continuity in care. These programs range in scope from large national programs to smaller community focused initiatives that have demonstrated increased coverage of health services particularly in remote areas and improved outcomes related to HIV and some non-communicable diseases.⁸⁰⁻⁸³ In these settings, the cost associated with these workers is relatively modest.

In India specifically, the National AIDS Control program has recognized the need for decentralizing services as well as the importance of navigators, who are analogous to community health workers, for improving HIV outcomes from testing to linkage to HIV viral suppression.⁸⁴ The National Program is already supporting a cadre of such staff in government-based testing and treatment centers and non-governmental organizations. Through partnership between USAID, the National AIDS Control Organization and investigators on this study team, India is also exploring home-based HIV testing and treatment. Moreover, India has a culture of DOT with TB treatment and current requirements for buprenorphine for OAT including daily pickups (including on Sundays).⁸⁵⁻⁸⁷

Thus, there is a precedent for the types of low-cost support interventions being evaluated in this trial. Moreover, formal cost analyses are planned as part of the parent grant and so will further inform adoption of these interventions by the Indian government and other LMIC settings.

7.3 Study Hypotheses

- Among PWID at elevated risk for treatment failure, PWID receiving the high intensity intervention will have significantly higher SVR than those receiving either the medium or low intensity interventions.
 - 1a. Among PWID at minimal risk of treatment failure, PWID receiving either the high or medium intensity intervention will have significantly higher SVR than those receiving the low intensity intervention.
- 2. Among PWID at elevated risk for treatment failure, PWID receiving the high intensity intervention will have significantly higher treatment completion than those receiving either the medium or low intensity interventions.
 - 2a. Among PWID at minimal risk of treatment failure, PWID receiving either the high or medium intensity intervention will have significantly higher treatment completion than those receiving the low intensity intervention.
- 3. Among PWID at elevated risk for treatment failure, PWID receiving the high intensity intervention will have significantly higher adherence than those receiving either the medium or low intensity interventions.
 - 3a. Among PWID at minimal risk of treatment failure, PWID receiving either the high or medium intensity intervention will have significantly higher adherence than those receiving the low intensity intervention.
- 4. HCV reinfection rates will be lower among clients who have high engagement with OAT.

5. Among HIV/HCV co-infected PWID, HIV viral suppression will be higher after achievement of HCV cure.

8. OBJECTIVES

The overall goal of this protocol is to evaluate whether HCV treatment outcomes (sustained virologic response, treatment completion, adherence) and post treatment outcomes (HCV reinfection, HIV viral suppression) in HCV mono- and HIV/HCV co-infected PWID can be optimized by tailoring treatment support in 7 PWID-focused integrated HIV/HCV prevention treatment centers.

8.1 Primary Objective(s)

To evaluate whether the intensity of treatment adherence support affects sustained virologic response rates in HCV mono- and HIV/HCV co-infected participants receiving HCV DAAs in PWID-focused centers.

8.2 Secondary Objective(s)

- 1. To evaluate whether the intensity of treatment adherence support affects HCV treatment completion rates.
- 2. To evaluate whether the intensity of treatment adherence support affects HCV treatment adherence.
- 3. To estimate the incidence and correlates of HCV reinfection among HCV mono- and HIV/HCV coinfected PWID who achieve HCV cure.
- 4. To evaluate the impact of HCV cure on HIV viral suppression among HIV/HCV coinfected PWID.

9. STUDY DESIGN

This is a 3-arm, individual-level randomized clinical trial, in which treatment assignment probabilities vary according to participants' estimated propensity for treatment failure at baseline (precision randomization). Minimal risk individuals have a higher likelihood of being allocated to lower intensity intervention and elevated risk individuals have higher likelihood of being allocated to higher intensity intervention. An estimated 3,000 persons will be enrolled and randomized at 7 integrated care centers (ICCs) across India across a duration of 18 – 24 months. All persons who are receiving care in one of the 7 YRGCARE ICCs, who are eligible for HCV treatment according to standard criteria and provide written informed consent will be screened for eligibility. Using a 'precision clinical trial' approach, HCV treatment adherence support will be assigned using an unbalanced allocation method weighted by an individual's propensity for treatment failure.

Data from these 7 ICCs on early ART refills/HIV viral suppression (3-6 months after ART initiation) will be used to develop and validate an algorithm to predict propensity for HCV treatment failure. The optimal cutoff for the algorithm will be based on the combination of data used to develop the algorithm and data from community-based samples in each of these sites. Prior to treatment initiation, each participant will undergo a questionnaire to capture information on barriers/ facilitators to treatment adherence identified in the prediction model in order to determine the propensity for HCV treatment failure (minimal or elevated risk). Based on preliminary analysis, groups will be defined by the median of the score (below the median: minimal risk; above the median: elevated risk), but this may be modified depending on performance of the final algorithm. Individuals will be preferentially randomized to the support level that matches their failure risk. Those at elevated risk for treatment failure will be randomized at an allocation ratio of 3:2:1 for Arm 3 (high intensity support), Arm 2 (medium intensity support) and Arm 1 (low intensity support), respectively. Conversely, those at minimal risk will be randomized at a ratio of 1:2:3 to Arm 3 (high intensity support), Arm 2 (medium intensity support) and Arm 1 (low intensity support), respectively. Participants and study staff will be blinded to the risk classification (minimal, elevated) but, because of the nature of the interventions, blinding to intervention assignment is not possible.

Arm 1: Low intensity intervention: We will dispense 28-day supplies of medication at baseline, 4 weeks, and 8 weeks. Participants will receive standard adherence counseling at entry and every refill pickup/home or field delivery. Participants will have access to all of the services available at the ICC including facilitated linkage to referrals as needed. Patient Navigators will routinely track clients who miss refill appointments in real-time using standard tracking measurements.

Arm 2: Medium intensity intervention: The medium intensity intervention will include standard of care dispensation of 28-day supplies of medication at baseline, 4 weeks and 8 weeks. Participants will be assigned to a PN and receive tailored patient navigation support for medication reminders, picking up medication refills (or home or field delivery of study medications), overcoming barriers as well as service linkage.

Arm 3: High intensity intervention: The high intensity intervention will involve patient-centered DOT with flexibility in terms of the frequency of pickup and the site of DOT (ICC, field-based) with a minimum of at least 1 observed dose per week. Participants in this arm will also receive PN support for overcoming barriers and service linkage similar to participants in Arm 2. The main differences between Arms 2 and 3 are: (i) medications will not be dispensed for more than one week at a time (to coincide with OAT dosing, where applicable); and (ii) ≥1 dose/week will be observed.

To measure adherence, brief surveys and pill counts will be conducted at each medication pick up/ drop off. In the high intensity intervention, a computerized system will track client doses that are observed using biometrics, including doses delivered in the field.

Persons will be treated for HCV according to the standard of care in India. Minimal laboratory monitoring will be used except when clinically indicated. Clients with decompensated cirrhosis will be excluded from treatment.

All HIV/HCV co-infected participants and those HCV mono-infected participants who achieve SVR will be followed post SVR assessment. These individuals will be followed every six months after the SVR assessment to assess HCV reinfection and HIV viral suppression (among HIV/HCV coinfected participants) for up to 48 months after SVR. In each ICC, an electronic health record (EHR) is already in place. This system captures information on general patient characteristics,

medical history including diagnoses, laboratory testing, and treatment received including systematic assessment of ART refills. The system is designed to capture information on care delivered in the ICC (e.g., OAT, SSP) and other government centers (e.g., TB treatment). All treatment dispensation, adherence, and treatment outcomes including HCV RNA testing will be captured in this database. Re-infection will be assessed using the Abbott ARCHITECT HCV Ag assay which is highly sensitive (97-100%) in identifying HCV RNA^{88,89} and in a small study of re-infection demonstrated 100% sensitivity/specificity of identifying recurrence of virus post-SVR.⁹⁰

10. STUDY POPULATION

The target population is PWID who are actively infected with HCV in each of the 7 study cities. Currently, there are 11,293 PWID who have registered for services at one off the 7 ICCs. **Table 10.1** describes the characteristics of current ICC clients (and potentially eligible study participants) in each of the 7 sites. Overall as of June 2019, 6,590 HCV antibody positive clients have been registered across the 7 ICCs. Additionally, ICCs register a median of 35 new clients per month.

Table 10.1. Description of current clients in 7 ICCs across India

	Nort	Northeastern India Northern India Cen		Northern India		tral India	
	Aizawl	Churachandpur	Amritsar	Ludhiana	New Delhi	Bilaspur	Kanpur
Clients (N)	2,055	837	1,573	3,430	910	1,569	919
Median age	28	34	28	26	27	27	34
% female	14.2	15.0	5.1	9.5	1.7	6.2	1.0
% on OAT	32.7	55.5	60.2	74.4	25.2	53.2	0
% inject past 6 mo	80.0	65.3	82.7	52.0	99.3	93.3	100
HCV antibody + (N)	1,113	409	1,098	2,014	566	838	552

10.1 Inclusion/Exclusion Criteria

10.1.1. Participant inclusion criteria

Participants must meet all of the following criteria to be included in the trial.

- 1. Registered for care at an ICC in one of the 7 field sites.
- 2. At least 18 years of age
- 3. History of injection drug use by self-report
- 4. Active HCV infection confirmed by a detectable HCV RNA by PCR (HCV RNA ≥ 30 IU/ml) within 90 days prior to study entry. HCV RNA will be measured by FDA-approved tests for quantifying HCV RNA at local laboratories that operate in accordance with Good Clinical Laboratory Practices (GCLP) and participate in appropriate external quality assurance programs. The YRGCARE laboratory, where the majority of testing will be done, uses the Abbott real time HCV RNA assay.
- 5. Liver disease stage defined as non-cirrhotic or compensated cirrhotic (metric/diagnostic criteria used for fibrosis staging) within 90 days prior to study entry as listed below:

FIB-4 <3.25 corresponding to no cirrhosis

OR

FIB-4 ≥3.25 AND Child-Turcotte-Pugh (CTP) Score ≤6 indicating CTP Class A corresponding to compensated cirrhosis.

NOTE: Individuals with decompensated cirrhosis will be excluded and referred to nearby medical gastroenterology centers where specialized treatment is available.

- 6. Eligible for HCV treatment (using standard eligibility criteria as per Indian National Association for the Study of Liver Disease [INASL] guidelines)
 - i. Albumin >3.0 g/dL
 - ii. Hemoglobin >8.0 g/dL for women; >9.0 g/dL for men
 - iii. Platelet count >50,000/mm³
 - iv. Calculated creatinine clearance (CrCl) using Cockcroft-Gault method >30 mL/min
 - v. Aspartate aminotransferase (AST/SGOT) <10 times the upper limit of the normal range (ULN)
 - vi. Alanine aminotransferase (ALT/SGPT) <10 times the ULN
 - vii. Total bilirubin <1.5 times the ULN for participants not on atazanavir (ATV) and <3 times the ULN for participants on ATV
 - viii. International normalized ratio (INR) <1.5 times the ULN
- 7. Life expectancy greater than 1 year (as determined by study clinician)
- 8. Willing to initiate HCV treatment
- 9. Agree to be randomized to an adherence support strategy and willingness to be contacted by study staff
- 10. Ability and willingness to provide written informed consent
- 11. Female participants of reproductive potential (defined as women who have not been post-menopausal for at least 24 consecutive months, i.e., who have had menses within the preceding 24 months, or women who have not undergone surgical sterilization, specifically hysterectomy and/or bilateral oophorectomy or bilateral salpingectomy) must have a negative serum or urine pregnancy test within 48 hours prior to study entry by an approved laboratory that has Good Laboratory Practices certification or its equivalent, or using a point-of-care (POC) test. The serum, urine or POC pregnancy test must have a sensitivity of at least 25 mIU/mL.
- 12. All female participants of reproductive potential must agree not to participate in a conception process (e.g., active attempt to become pregnant or to impregnate, sperm donate, in vitro fertilization,) while on study treatment and for 6 weeks after stopping protocol-specified medication.
- 13. When participating in sexual activity that could lead to pregnancy, all female participants of reproductive potential must agree to use at least one reliable form of contraceptive while receiving protocol-specified medication, and for 6 weeks after stopping the medication. Such methods include:

- Condoms with or without a spermicidal agent
- Diaphragm or cervical cap with or without spermicidal agent
- Intrauterine device (IUD)
- Hormone-based contraceptive
- Tubal ligation
- 14. Female participants who are not of reproductive potential (women who have been postmenopausal for at least 24 consecutive months or have undergone hysterectomy and/or bilateral oophorectomy) are eligible without requiring the use of contraceptives. Male participants do not need to provide information on their female partner's reproductive potential.

All laboratory-based screening criteria must be measured within 90 days of the Entry Visit into the Trial with the exception of a pregnancy test for women which must be conducted 48 hours prior to study entry.

10.1.2. Participant exclusion criteria

Participants meeting any of the following criteria will be excluded from study participation.

- 1. Psychologically unfit to provide written informed consent
- 2. Planning to migrate within the next six months
- Known allergy/sensitivity or any hypersensitivity to components of study drug(s) or their formulation.
- 4. Acute or serious illness requiring systemic treatment and/or hospitalization within 30 days prior to study entry.
- 5. In HIV positive participants, presence of active or acute AIDS-defining opportunistic infections within 30 days prior to study entry.
 - NOTE: AIDS-defining opportunistic infections as defined by the Centers for Disease Control and Prevention (CDC) found in the following document: http://www.cdc.gov/mmwr/preview/mmwrhtml/00018871.htm
- 6. Use of prohibited medications within the past 14 days prior to study entry (please refer to **Section 11.2.6** for the list of prohibited medications).
- 7. Evidence of decompensated liver disease on clinical exam
- 8. Evidence of active tuberculosis
- 9. Evidence of chronic hepatitis B infection (HBsAg positive)
- 10. Currently on HCV treatment

- 11. Prior history of DAA-based HCV treatment
- Confirmed active SARS CoV-2 infection or suspected active SARS CoV-2 infection at enrollment
- 13. Currently nursing (breastfeeding)

10.1.3. Co-enrollment criteria

HIV positive participants may be co-enrolled in the "ICC+ Study: Strategies to improve the HIV care continuum in key populations in India [DA041034]." Co-enrollment does not require permission from anyone on the protocol committee. Special attention should be paid to the timing of blood draws such that there is at least 2 weeks between blood draws for the two studies.

For co-enrollment in any other protocol, site clinicians should first check with the study Principal Investigators (PIs).

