allocation ratio using stratified, restricted randomization. PWID and MSM-focused ICCs were initiated in 11 intervention sites in June 2014. Venues (non-governmental organizations [NGOs] or government facilities) were selected for scale-up following discussions between the Indian government, NGO leaders, community members, and investigators. In the PWID stratum of this trial, ICCs were scaled from existing opioid agonist treatment (OAT) centers to incorporate other risk reduction services including syringe services programs (SSP) and HIV counseling and testing (HCT). Some medical services at these ICCs are provided on-site including sexually transmitted infection (STI) treatment while others are provided through peer navigated referral (e.g., tuberculosis treatment, antiretroviral therapy [ART]).

After 2 years, a second (post-intervention) RDS was conducted in all 22 sites from October 2016 and May 2017. ICCs resulted in significant improvements in HIV testing, but limited ART uptake.²⁸ In response, we launched a second phase to evaluate supplementing ICCs with demand-side incentives for HIV care (DA041034; ClinicalTrials.gov identifier: NCT02969915). Of the prior sites,

16 were selected based on HIV prevalence and poor care engagement (8 PWID, 8 MSM). ICCs have been scaled in all cities with half randomized to receive incentives for HIV care. A third cross-sectional sample will be accrued in late 2020 to evaluate community impact of the incentives. This protocol will take place in 7 of the 8 PWID ICCs in this ongoing trial (**Figure 7.1.1**). One of the 8 sites is being excluded due to low HCV prevalence.

7.1.4. High burden of HCV among PWID in India but poor engagement across the HCV care continuum

In the 2013 baseline assessment for the aforementioned trial, 14,481 PWID were recruited in 15 cities (~1000 per city) across India.²⁹ HCV prevalence ranged from 4.9 – 64.9% in the 15 cities.³⁰ Only 1,272 (7%) had ever been tested for HCV and the most common reason for not having been tested was never having heard of HCV (51%)

followed by low risk perception. Of 5,777 PWID with evidence of HCV infection, only 5.6% were aware of their HCV positive status. In 2016, at the evaluation survey, HCV prevalence ranged from 37.2 to 76.6% in the 7 proposed sites (**Figure 7.1**).

[figure not shown]

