Annual assessments of HIV viral load among HIV/HCV coinfected participants in the 7 ICCs are expected as part of other ICC activities and standard of care at Indian government ART centers. All available viral load measurements for HIV/HCV co-infected PWID enrolled in the trial will be used. Viral suppression will be defined as HIV RNA less than LLOQ. We will compare viral suppression across two groups defined by primary outcome status, which will be cured vs. not cured using logistic regression with generalized estimating equations (GEE) to account for repeated measures within individuals. Because these groups will be defined by the primary outcome and no longer balanced by randomization, analysis will be adjusted for confounding factors including demographics, substance use, needle sharing, MOUD, SSP use, social support and frequency of visits to the ICC. Analyses will be combined across all groups but we will include a covariate for the classification of risk of treatment failure (minimal or elevated) and intervention received. In order to account for missing data due to loss-to-follow-up, we will use inverse-weighting methods.^{4,5}

2d.1. Sensitivity analyses. We will vary the threshold for HIV viral suppression (<150 copies/ml vs. 400 copies/ml vs. 1000 copies/ml) and will also incorporate the revised definition of SVR vs. treatment failure using sequence data.

3. Exploratory analysis

3a. Impact of interventions on medication for opioid use disorder (MOUD) utilization. Daily MOUD utilization data is available in the electronic health record. We will explore the impact of the interventions within strata by arm on new MOUD initiation and MOUD retention using methods of survival analysis, logistic regression with GEE and growth mixture models. Analyses will be adjusted for site. Additional sensitivity analyses will be similar to those reported in the primary and secondary outcome analyses and will include accounting for the prognostic score.

3b. Impact of interventions on quality of life.

Quality of life data is captured at the SVR visit and at semi-annual post-treatment follow-up visits. Using logistic and linear regression with GEE, we will explore the impact of interventions within strata on quality of life after treatment.

3c. Impact of interventions on mortality.

Using Poisson regression, we will explore the impact of interventions within strata on all-cause mortality.

3d. Effect of delays in treatment completion on SVR.

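### The cured versus not-cured comparison of HIV suppression (SAP 2d) names no site term, so differences between cities, including a randomized HIV-care incentive, can confound it in either direction

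*Protocol*

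**What the plan says.** **The overlapping trial.** Protocol Section 7.1.3 describes a second-phase trial, begun because ART uptake had been limited, and says: "ICCs have been scaled in all cities with half randomized to receive incentives for HIV care". STOP-C uses the same centers: "This protocol will take place in 7 of the 8 PWID ICCs in this ongoing trial". On timing, the section says only: "A third cross-sectional sample will be accrued in late 2020 to evaluate community impact of the incentives".

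**Co-enrolment.** Under Protocol Section 10.1.3, "HIV positive participants may be co-enrolled in the" ICC+ study, and "Co-enrollment does not require permission from anyone on the protocol committee". The one condition is blood-draw spacing ("Special attention should be paid to the timing of blood draws such that there is at least 2 weeks between blood draws"). Any other protocol requires a check with the study PIs.

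**The analysis.** For HIV suppression, SAP 2d states: "We will compare viral suppression across two groups defined by primary outcome status, which will be cured vs. not cured", by logistic regression with GEE. It acknowledges that these groups are not balanced by randomization, and continues: "analysis will be adjusted for confounding factors including demographics, substance use, needle sharing, MOUD, SSP use, social support and frequency of visits to the ICC". Risk stratum and intervention received are added as covariates. The listed sensitivity analyses change the HIV RNA threshold or the SVR definition. Protocol Section 15.7.2.2 has a similar list, opened by a general commitment to account for all known potential confounders.

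**Site elsewhere.** SAP 1, 2a and 2b adjust for site as a fixed effect, with random-effect and unadjusted versions as sensitivity analyses. SAP 3a also adjusts for site. SAP 2d does not mention it.

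**The concern.** Randomization protects the comparisons between support arms. It does not protect a comparison of people who were cured with people who were not. Anything that varies by city and is related to both SVR and HIV suppression will enter the pooled contrast unless the model removes it.

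City is a strong candidate on the protocol's own description. Incentives for HIV care were assigned by city and aim at the area in which this outcome lies. Apart from incentives, Protocol Table 10.1 shows OAT coverage from 0% (Kanpur) to 74.4% (Ludhiana) and recent injecting from 52.0% (Ludhiana) to 100% (Kanpur). Section 11.1.1.3 says ART is dispensed on site at some centers and through government centers at others. Individual OAT and drug-use covariates may absorb part of this, but nothing in the list captures how ART is delivered or whether the city had incentives.

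There is also a route to SVR. The primary analysis counts a missing SVR result as failure. If that status is carried into SAP 2d, whatever changes attendance at the SVR visit by city also changes who is labelled cured.

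At stake is the reading of secondary objective 4. A city effect could be reported as an HIV benefit of HCV cure, or could hide a real one.

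**Working it through.** The documents give no sample size, power or effect size for this analysis, so there is no figure to reproduce. The check has two parts.

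**1. Covariates named, side by side**

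| Model | Contrast | Site named? |
|---|---|---|
| SVR (SAP 1) | randomized arms | yes, fixed effect |
| Completion (SAP 2a) | randomized arms | yes, fixed effect |
| Adherence (SAP 2b) | randomized arms | yes |
| HIV suppression (SAP 2d) | cured vs not cured | no |

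City, incentive assignment and ICC+ co-enrolment are not named in SAP 2d or in the matching paragraph of Protocol Section 15.7.2.2.

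**2. How large a spurious contrast could be**

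Take two groups of cities, incentive (1) and other (0). Let *w* be the share of co-infected participants in incentive cities, *c* the proportion cured and *s* the proportion suppressed. Assume cure has no effect on suppression within a city. Then:

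- P(suppressed | cured) = [w·c1·s1 + (1−w)·c0·s0] / [w·c1 + (1−w)·c0]
- P(suppressed | not cured) = [w·(1−c1)·s1 + (1−w)·(1−c0)·s0] / [w·(1−c1) + (1−w)·(1−c0)]

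All values of *c* and *s* are assumptions. The split of the seven cities is not stated. If the eight PWID sites were divided evenly, it is 3:4 or 4:3.

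*SVR higher in incentive cities.* w = 4/7, c = (0.90, 0.80), s = (0.70, 0.50):
- Cured: (4×0.90×0.70 + 3×0.80×0.50) / (3.6 + 2.4) = 3.72/6.0 = 62.0%
- Not cured: (4×0.10×0.70 + 3×0.20×0.50) / (0.4 + 0.6) = 0.58/1.0 = 58.0%
- Difference +4.0 points; OR = (0.62/0.38)/(0.58/0.42) = 1.18

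*SVR lower in incentive cities.* w = 3/7, c = (0.80, 0.90), s = (0.70, 0.50):
- Cured: (3×0.80×0.70 + 4×0.90×0.50) / (2.4 + 3.6) = 3.48/6.0 = 58.0%
- Not cured: (3×0.20×0.70 + 4×0.10×0.50) / (0.6 + 0.4) = 0.62/1.0 = 62.0%
- Difference −4.0 points; OR = (0.58/0.42)/(0.62/0.38) = 0.85

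*SVR equal.* c = (0.85, 0.85): difference 0, OR 1.00, whatever the suppression rates.

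*A wider grid with SVR higher in incentive cities.* w = 1/2, suppression 75–85% versus 65–70%, cure 88–92% versus 80–85%. The extremes are:
- Smallest, s = (0.75, 0.70), c = (0.88, 0.85): 1.255/1.73 = 72.5% against 0.195/0.27 = 72.2%, so 0.3 points, OR 1.02
- Largest, s = (0.85, 0.65), c = (0.92, 0.80): 1.302/1.72 = 75.7% against 0.198/0.28 = 70.7%, so 5.0 points, OR 1.29

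Across these scenarios the crude odds ratio runs from 0.85 to 1.29. Within each city group it is 1.00 by construction, which is what a site-adjusted model would target.

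**The case against.** **The covariate lists are open-ended.** SAP 2d introduces its list as inclusive, and the protocol promises to account for all known potential confounders. This stands: the plan permits a site term. But it does not name one, and an analyst who follows the named list would leave city out.

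**No document shows that SVR differs by incentive city.** This also stands. Protocol Section 7.1.3 says only that the incentives are for HIV care. STOP-C pays for the SVR visit at every site (Section 18.7) and traces missed visits everywhere (Section 10.3), which would tend to even out attendance. Without a difference in SVR there is no bias, so the point is conditional.

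**Visit frequency may stand in for incentives.** Only in part. Incentives may themselves change it, and it need not reflect their effect on ART refills or suppression.

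**The incentives may have ended.** The documents do not say. Their evaluation was planned for late 2020, yet the protocol, with a page dated June 2022, still allows ICC+ co-enrolment. The other city differences remain either way.

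**A stronger inference.** A reader might conclude that open co-enrolment is itself the flaw. The documents do not support that. The permission waiver covers HIV-positive participants and one named study, with a spacing rule. The incentive was assigned by city, so requiring permission would not remove the confounding.

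**Conclusion.** The point holds as a gap in pre-specification with a plausible route to bias. SAP 2d pools a non-randomized contrast over cities that differ by design and in practice, and does not name site.

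The size is unknown. The range of 0.85 to 1.29 rests on assumed rates, two groups of cities, no true effect of cure, and no adjustment for the covariates that the SAP does plan. The adjusted bias could be smaller. It is zero if SVR does not vary by city.

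Two further readings go too far. One is that the analysis will overstate the benefit of cure: the direction depends on whether SVR is higher or lower in incentive cities, which the documents do not show. The other is that the main result is at risk: the primary SVR comparison is randomized within risk strata and adjusted for site, so it is not affected. This is a low-severity improvement to one secondary analysis.

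**What to change.** In SAP 2d, and in the matching paragraph of Protocol Section 15.7.2.2:

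- Name site as a fixed effect in the GEE model. A city's incentive assignment that is constant over follow-up is then absorbed, along with other stable city differences.
- If incentives started or stopped in any city during follow-up, add a site-by-period term.
- Add a sensitivity analysis by city incentive assignment. Assignment cannot be estimated as a main effect beside site terms, so either let it replace site or examine the cure contrast separately in incentive and other cities.

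The cost is a few lines of SAP text and six indicator terms for seven sites. Site is already recorded and determines the city's assignment, so no new data collection is needed. Some precision may be lost where a site has few co-infected participants who were not cured; the documents do not give those numbers.
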